10.3 Exploratory Efficacy Analyses

10.3.1 Patient-reported Outcome

Patient reported outcome endpoints by FACT-P and BPI-SF will be summarized according to their respective scoring manuals.

Analgesic drug score will be recorded according to the World Health Organization (WHO) scale (0 for no medication, 1 for non-opioid pain medication, 2 for opioids for moderate pain, and 3 for opioids for severe pain).

Analyses of change and/or percent change from baseline will be analyzed for each scheduled post-baseline visit and for the final visit for the EQ-5D-5L VAS.

Patients who do not have both a baseline measurement and at least one post-baseline measurement will not be included.

PRO endpoints will be summarized for all patients and may also be summarized for the subgroups of patients defined by measurable disease status at baseline.

BPI-SF

The primary analysis of change in pain intensity over time will be assessed using BPI-SF Item #3 (pain symptoms at their worst over the last 24 hours). A composite assessment of change in pain intensity (Item #3-6, worst pain, least pain, average pain, and current pain, respectively) will also be analyzed.

BPI item scores, change from baseline, and percentage change from baseline in daily pain intensity will be summarized at each visit and at the final visit using descriptive statistics (N, mean, SD, minimum, median, and maximum).

Longitudinal plots of the mean changes from baseline to each scheduled visit may also be presented. These plots may exclude visits for which only a small percentage (e.g., $\leq 30\%$) of patients have data.

FACT-P

Scores and post-baseline score changes for the FACT-P global, physical, functional, and prostate-cancer scale scores as well as scores for the FACT-P trial outcome index (TOI) will be summarized at each visit and at the final visit using descriptive statistics (N, mean, SD, minimum, median, and maximum).

Longitudinal plots of the mean changes from baseline to each scheduled visit may also be presented. These plots may exclude visits for which only a small percentage (e.g., $\leq 30\%$) of patients have data.

EQ-5D-5L

Change and percent change from baseline will be analyzed at each visit and at the final visit for EQ-5D-5L VAS. Patients who do not have both a baseline measurement and at least one post-baseline measurement will not be included.

10.3.2 Changes in Tumor Samples and Changes in Circulating Tumor DNA

The relationship between rucaparib activity and gene mutations identified from testing the available tissue and plasma samples will be evaluated. Additional genomic or transcriptional signatures may also be evaluated. Analyses will be described using graphical plots and descriptive statistics.

10.3.3 Concordance of HRR gene status between Metastatic Disease Site Biopsy, Archival Primary Tissue and Plasma ctDNA

Pairwise comparisons will be performed using available plasma and tissue (including archival and metastatic) test results to explore the concordance in HRR gene alterations.

10.3.4 ORR and/or PSA Response in Relation to Germline/Somatic Status

The ORR and/or PSA response rate will be analyzed for the subgroups of patients with a germline or a somatic BRCA1/2 alteration.

10.3.5 Time to First Subsequent Antineoplastic Therapy

Time from date of last dose of study drug to first subsequent antineoplastic therapy will be summarized using a Kaplan-Meier plot and descriptive statistics.

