4.3 Exploratory Objectives

Exploratory objectives in this study are:

- To evaluate patient reported outcomes (PRO) using the EuroQol 5 dimensions 5 level questionnaire (EQ-5D-5L), Functional Assessment of Cancer Therapy-Prostate (FACT-P), analgesic drug score, and Brief Pain Inventory – Short Form (BPI-SF) instruments
- To assess changes in the molecular profile over time of matched pre- and post-treatment tumor or plasma samples
- To assess concordance in HRR gene mutation status in matched Pre-Screening biopsy tissue, archival primary and metastatic tumor tissue, and plasma circulating tumor DNA (ctDNA)
- To assess ctDNA as a molecular marker of response

- To assess time to first subsequent antineoplastic therapy
- To evaluate loss of heterozygosity (LOH) in metastatic disease site biopsy and archival primary and metastatic tumor tissue samples
- To evaluate mechanisms of response and resistance in ctDNA and progression tumor tissue samples

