11.5.3.4 Time to First Subsequent Antineoplastic Therapy

Time to first subsequent antineoplastic therapy will be summarized using a Kaplan-Meier plot and descriptive statistics.

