To assess time to PSA progression	Time from first dose of rucaparib to the date that a \geq 25% increase and absolute increase of \geq 2 ng/mL above the nadir is observed, confirmed by a consecutive measure at least 3 weeks later
To assess the safety and tolerability of rucaparib	The incidence of adverse events (AEs), clinical laboratory abnormalities, dose modifications, vital signs, ECGs, physical examinations, and ECOG performance status
To characterize the steady-state pharmacokinetics (PK) of rucaparib	Trough level plasma rucaparib concentrations (C_{min})

Exploratory Objectives	Exploratory Endpoints
To evaluate patient reported outcomes (PRO) using the EuroQol 5 dimensions questionnaire (EQ-5D-5L), Functional Assessment of Cancer Therapy – Prostate (FACT-P), analgesic drug score, and Brief Pain Inventory – Short Form (BPI-SF) instruments	Change and/or percent change from baseline for the EQ-5D-5L instrument. FACT-P and BPI-SF summarized according to their respective scoring manuals. Analgesic drug score recorded according to the World Health Organization (WHO) scale.
To assess changes in the molecular profile over time of matched pre- and post-treatment tumor and plasma samples	Changes in cancer-related mutations detected in plasma and tissue samples.
To assess concordance in HRR gene mutation status in matched screening biopsy tumor tissue, archival primary and metastatic tumor tissue and plasma ctDNA	Pairwise comparisons of available tissue and plasma HRR testing results.
To assess ctDNA as a molecular marker of response	Target lesion and/or PSA dynamics in relation to available longitudinal ctDNA test results.
To assess time to first subsequent antineoplastic therapy	Kaplan-Meier plot and/or descriptive statistics.
To evaluate loss of heterozygosity (LOH) in metastatic disease site biopsy and archival primary and metastatic tumor tissue samples	Concordance between percentage genomic loss of heterozygosity (%LOH) in available archival primary and metastatic tumor tissue samples.
To evaluate mechanisms of response and resistance in ctDNA and progression tumor tissue samples	Target lesion and/or PSA dynamics in relation to available plasma and tissue test results.

[figure not shown]

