10.2.2 Radiographic PFS

rPFS is defined as the time from first dose of rucaparib to the date of first objective evidence of radiographic progression (soft tissue or bone lesion) or death due to any cause, whichever occurs first, plus 1 day. Radiographic disease progression includes confirmed bone disease progression and soft tissue disease progression adjudicated by IRR using the PCWG3 guidelines for bone disease and modified RECIST Version 1.1 for soft tissue disease. Patients without a documented event of progression will be censored on the date of their last adequate tumor assessment (i.e., radiographic assessment) or date of first dose of study drug if no post-baseline tumor assessments have been performed.

Patients who withdraw from treatment prior to radiographic progression will be followed for disease status and survival whenever possible. Only tumor scans (and deaths, for PFS analyses) prior to start of any subsequent anticancer treatment will be included. If a patient discontinues study drug due to a reason other than radiographic PD and subsequently begins another anticancer therapy (ACT) prior to a PFS event, that patient will be censored at the last scan prior to the start of ACT. However, scans/PFS events occurring more than 24 weeks after DC/stop of study drug and more than 24 weeks after their last previous scan but prior to start of subsequent ACT will not be included in the analysis and such patients will be censored at their last scan prior to the end of the 24-week window.

rPFS will be presented by gene mutation for all patients (separately, using IRR and Investigator assessments) and may also be presented by measurable disease status at Baseline.

A sensitivity analysis will be performed in which patients who have discontinued without radiographic progression, but who have had PSA progression, will be treated as having an event at the time of PSA progression.

rPFS will be summarized using Kaplan-Meier methodology and in the case of a low censoring rate it may be summarized with descriptive statistics.

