10.2.3 Overall Survival

OS is defined as the date from first dose of rucaparib to the date of death due to any cause, plus 1 day. OS will be summarized using the Safety Population, by gene mutation and Overall, using Kaplan-Meier methodology. OS may also be summarized for the subgroups of

patients defined by measurable disease status at baseline. In the case of a low censoring rate OS may be summarized with descriptive statistics.

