10.2.6 Time to PSA progression

Time to PSA progression is defined as the time from first dose of rucaparib to the date that a $\geq 25\%$ increase and absolute increase of ≥ 2 ng/mL above the nadir (or baseline if there was no PSA decline after baseline) in PSA was measured, plus 1 day. The increase must be confirmed by a second consecutive assessment conducted at least 3 weeks later (unless the PSA progression occurred at the last recorded PSA assessment). If confirmed, the date used for time of PSA progression is the earlier of the 2 PSA dates. Additionally, early rises (before 12 weeks following first dose of study drug) are not considered in determining PSA progression.

Time to PSA progression will be summarized for all patients and may also be summarized for the subgroups of patients defined by measurable disease status at baseline.

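### SAP 10.3.5 counts time to first subsequent antineoplastic therapy from the last rucaparib dose, so it measures only the off-treatment gap, is undefined for patients still on drug at a cut-off, and has no censoring rule

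*SAP*

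**What the plan says.** The protocol lists the endpoint among its exploratory objectives (section 4.3): "To assess time to first subsequent antineoplastic therapy". Its analysis section, 11.5.3.4, says only how the result is displayed: "Time to first subsequent antineoplastic therapy will be summarized using a Kaplan-Meier plot and descriptive statistics". Neither place gives a time origin. The objectives table in SAP 2.1 also names only the display: "Kaplan-Meier plot and/or descriptive statistics".

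The origin appears in one place, SAP 10.3.5: "Time from date of last dose of study drug to first subsequent antineoplastic therapy". SAP 9.3 lists the endpoint under exploratory efficacy variables.

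Three other time-to-event endpoints in the SAP start at first dose:

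- SAP 10.2.2: "rPFS is defined as the time from first dose of rucaparib to the date of first objective evidence of radiographic progression"
- SAP 10.2.3: "OS is defined as the date from first dose of rucaparib to the date of death due to any cause"
- SAP 10.2.6: "Time to PSA progression is defined as the time from first dose of rucaparib"

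SAP 11.1 states that the censoring rules are set out under the individual time-to-event endpoints. Section 10.3.5 contains none. SAP section 13, which records departures from the protocol and added detail, does not mention this endpoint.

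**The concern.** An efficacy variable with this name would ordinarily be read as showing how long treatment deferred the next therapy. Anchored at last dose it cannot show that, because all time on rucaparib lies outside the interval. This includes any treatment beyond progression allowed under Protocol 7.4.4. What remains is the delay between stopping one drug and starting another.

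Two consequences follow. A patient who has not stopped rucaparib has no origin, so at a data cut-off he either drops out of the analysis or needs a rule that is not written. Among patients enrolled at the same time, those still on drug are by construction the ones treated longest. Also, without censoring rules, two programmers could draw different Kaplan-Meier curves from the same data and both comply with the SAP.

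At stake is how one exploratory result is interpreted and reproduced. No hypothesis test depends on it.

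**Working it through.** The plan gives no figure for this endpoint, so there is none to reproduce. The check compares definitions, then illustrates the difference with assumed durations.

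**1. Origins and censoring side by side.**

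| Endpoint | Origin | Censoring rule in its own section |
|---|---|---|
| Radiographic PFS (SAP 10.2.2) | first dose | yes |
| Overall survival (SAP 10.2.3) | first dose | not stated |
| Time to PSA progression (SAP 10.2.6) | first dose | not stated |
| Duration of response (SAP 10.2.1) | first response | yes |
| First subsequent therapy (SAP 10.3.5) | last dose | not stated |

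**2. What the interval contains.** Let T be time on rucaparib and G the gap from last dose to next therapy.

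- SAP 10.3.5 value = G
- Value from first dose = T + G

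T does not enter the SAP value. If T changes and G does not, the endpoint does not move.

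**3. Size of the difference (assumed durations).** Take T and G as independent exponentials, with a median gap of 1.5 months, and simulate 200,000 patients.

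| Median time on drug | Median, SAP origin | Median, first-dose origin |
|---|---|---|
| 5 months | 1.5 | 7.4 |
| 10 months | 1.5 | 12.3 |

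Doubling time on drug adds 12.3 − 7.4 = 4.9 months on the first-dose scale and nothing on the SAP scale.

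**4. Patients with no origin.** SAP 10.2.4 computes clinical benefit rates relative to a visit cut-off, and SAP 2.3 foresees a regulatory filing before Cohort A (BRCA1/2) is fully enrolled. Analyses while some patients are still on drug are therefore foreseeable. Assume uniform accrual over 24 months, exponential time on drug with median m, and a cut-off F months after accrual ends. With λ = ln 2 / m:

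share still on drug = [exp(−λF) − exp(−λ(24 + F))] / (24λ)

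- m = 4, F = 12: λ = 0.1733; (0.1250 − 0.0020) / 4.159 = 0.030
- m = 10, F = 6: λ = 0.0693; (0.6598 − 0.1250) / 1.664 = 0.32

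Across m from 4 to 10 months and F of 6 or 12 months, the share runs from about 3% to 32%. These patients have no value under SAP 10.3.5. Counted from first dose, all of them enter the risk set and are censored.

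**5. Situations with no rule.** Section 10.3.5 does not cover three cases: still on rucaparib, off rucaparib and alive without next therapy, and dead before next therapy. The third matters most. If deaths are censored, one minus the Kaplan-Meier estimate overstates the proportion of patients who actually start a next therapy. If deaths count as events, the endpoint is a composite and should be named as one.

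**The case against.** The strongest reply is that the SAP states its origin openly and contradicts nothing. The protocol is silent on the origin, so a reader who infers a conflict between the two documents goes further than the text allows. Last dose is also the anchor for collecting subsequent treatments (Protocol 9.6.3), and an off-treatment interval is a legitimate thing to describe. Benefit on drug is reported elsewhere, through treatment duration, duration of response, radiographic PFS, overall survival and clinical benefit rate. Nor do all the SAP's time-to-event endpoints start at first dose: duration of response starts at first response. All of this stands. It limits the weight of the point but does not make the off-treatment gap a measure of deferral.

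A reader might go further and infer that the endpoint ranks patients backwards. The arithmetic allows it. A patient with 12 months on drug and a 1-month gap scores 1, and one with 2 months on drug and a 4-month gap scores 4; from first dose they score 13 and 6. But no planned analysis ranks patients on this variable. The study has no comparator arm, the output is a curve with descriptive statistics, and the SAP never says that longer is better. The durations are invented, so how often an order would reverse is unknown.

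A reader might also infer that patients on drug lack an origin at every analysis. Protocol 5.3 closes the study once all patients have stopped treatment and had the 28-day visit. The gap therefore arises at earlier cut-offs, and for patients who move to the extension protocol described in the same section.

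Finally, the missing censoring rule is not peculiar to this endpoint, as the table shows. It matters more here because death before next therapy can be handled in several defensible ways that give different curves.

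**Conclusion.** The point holds as a minor defect of definition. As written, SAP 10.3.5 measures the off-treatment gap, does not reflect how long rucaparib defers the next therapy, and gives no value for patients still on drug at a cut-off before closure or moving to the extension. The absent censoring rule falls short of what SAP 11.1 promises.

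These statements follow from the text and need no assumed numbers. The figures of 1.5 against 7.4 and 12.3 months, and of 3% to 32% without an origin, rest on assumed exponential durations; the medians also assume independence of T and G, and the shares uniform accrual. They show what is possible in this setting, not what will be observed. The endpoint is exploratory and untested, so no primary or secondary result changes.

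**What to change.** Rewrite SAP 10.3.5 as follows:

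1. Define the endpoint as the time from first dose of rucaparib to the start of first subsequent antineoplastic therapy, in all treated patients.
2. Censor patients alive without subsequent therapy, including those still on rucaparib, at last contact or the data cut-off.
3. State how death before next therapy is handled. Either count it as an event and name the endpoint time to first subsequent therapy or death, or treat it as a competing risk and show a cumulative incidence curve in place of the Kaplan-Meier plot.
4. Record the change in SAP section 13 and align the entry in the SAP 2.1 table.
5. If the gap from last dose to next therapy is wanted, report it under its own name as a descriptive summary in patients who have stopped.

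The cost is a short SAP edit and its programming. No new data are needed: first dose is Study Day 1, and subsequent treatments are already collected at the 28-day visit (Protocol 9.6.2) and every 12 weeks in long-term follow-up (Protocol 9.6.3).

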10.3.6 Genomic Loss of Heterozygosity (%LOH)

The percentage genomic loss of heterozygosity (% LOH) will be determined from all tissue samples with adequate sequencing data. The concordance between % LOH in archival and metastatic samples will be evaluated. The relationship between % LOH and response to rucaparib may also be explored.

10.3.7 Change from Baseline in PSA

Best change from baseline in PSA at any time will be presented using a waterfall plot.

10.4 Exploratory Pharmacokinetic Analyses

In all patients with at least one PK sample collected, the trough plasma rucaparib PK data (C_{\min}) and summary statistics (N, mean, SD, minimum, median, max, CV%) will be reported. The PK data and selected safety and efficacy endpoints will be included in exploratory population PK and exposure-response analyses, and the results will be reported separately.

11 STATISTICAL / ANALYTICAL ISSUES

11.1 Handling of Dropouts or Missing Data

All data will be used to their maximum possible extent but without any imputations for missing data. All time to event analyses include censoring and the rules for deriving the censoring value are described in more detail under each one of the time to event endpoints.

11.2 Pooling of Centers in Multi-Center Studies

The centers within a given region (e.g., United States versus Rest of World) will be pooled, if applicable.

11.3 Multiple Comparison / Multiplicity

No adjustments for multiple comparisons will be made.

11.4 Interim Analysis and Data Monitoring

A DMC has been incorporated into the Study conduct to provide review and assessment of the safety and efficacy data, in a systematic manner and to safeguard the interest and the safety of the participating patients in the Study. The DMC is tasked with regularly reviewing the safety and efficacy of the Study to ensure a favorable risk-benefit ratio for the patients. A separate DMC charter contains the details regarding the membership and activities of the DMC.

Simon 2-stage designs have been employed in each sub-cohort to allow futility analyses to be conducted to help assess whether each sub-cohort should proceed to full enrollment. The Sample Size Justification section ([Section 2.3](#)) contains additional detail regarding the Simon 2-stage assumptions and parameters.

Cohort A

Cohort A will be divided into 2 sub-cohorts defined by deleterious gene mutation (BRCA1/2 vs. ATM).

Cohort A (BRCA1/2)

A Simon 2-stage design to evaluate confirmed ORR by modified RECIST Version 1.1 criteria per investigator will be used. With rolling enrollment, after the first 37 patients have either: a) completed 16 weeks of treatment, or b) discontinued treatment prior to completing, an analysis will be performed (i.e., Stage 1). If $\leq 8/37$ patients in Stage 1 have a confirmed objective response (CR or PR per investigator and without progression in bone per PCWG3), the DMC will evaluate the overall risk benefit for study treatment and make a recommendation whether further enrollment should be discontinued. If $\geq 9/37$ patients have a confirmed objective response, then enrollment will continue with additional patients in Stage 2. The parameters of the Simon 2-stage design would accrue a total of 83 patients in this sub-

cohort. If there were at least 23 responses in 83 patients, the null hypothesis (ORR = 20%) would be rejected.

Note: If the study is to proceed to Stage 2, additional patients with a deleterious BRCA1/2 mutation up to 100 total patients may be enrolled in Cohort A (BRCA1/2) if additional clinical data is requested by the regulatory authorities to support regulatory filing. If sufficient evidence exists to support a regulatory filing prior to fully enrolling Cohort A (BRCA1/2), enrollment may be discontinued early.

Cohort A (ATM)

Patients in Cohort A (ATM), having a deleterious ATM mutation, will be enrolled concurrently with patients from Cohort A (BRCA1/2). It is expected that about 1/3 of the Cohort A patients will have deleterious ATM mutations. If 100 patients are enrolled in Cohort A (BRCA1/2), then approximately 50 patients would be expected to enroll into Cohort A (ATM).

A Simon 2-stage type futility rule will be employed in Cohort A (ATM). The Stage 1 analysis will be performed after the first 31 patients have either: a) completed 16 weeks of treatment; or b) discontinued treatment prior to completing. Enrollment into the study will continue while this analysis occurs. If $\leq 6/31$ patients in Stage 1 have a confirmed objective response (CR or PR per investigator and without progression in bone per PCWG3), the DMC will evaluate the overall benefit/risk for patients with deleterious ATM mutations in this cohort and make a recommendation whether further enrollment should be discontinued. If $\geq 7/31$ patients have a confirmed objective response, then enrollment will continue in Stage 2. If the study is to proceed to the second stage, additional patients with a deleterious ATM mutation may be accrued for a total of approximately 50, dependent upon the enrollment of Cohort A (BRCA1/2). If there are at least 16 responses in 53 patients with a deleterious ATM mutation, the null hypothesis (ORR = 20%) would be rejected.

Cohort B

Cohort B will be divided into 2 sub-cohorts defined by deleterious gene mutation (BRCA1/2 vs. ATM). Cohort B will be enrolled concurrently with Cohort A and is expected to enroll at approximately the same rate as Cohort A. Enrollment in Cohort B will be halted when Cohort A (BRCA1/2) is fully enrolled.

Cohort B (BRCA1/2)

Up to approximately 100 patients may be enrolled into Cohort B (BRCA1/2), dependent upon enrollment in Cohort A (BRCA1/2). As in Cohort A, a Simon 2-stage type futility rule will be employed. The Stage 1 analysis will be performed after the first 19 patients have either: a) completed 16 weeks of treatment; or b) discontinued treatment prior to completing. Enrollment into the study will continue while this analysis occurs. If $\leq 4/19$ patients in Stage 1 have a PSA response ($\geq 50\%$ decrease), the DMC will evaluate the overall risk benefit for study treatment. If $\geq 5/19$ patients have a PSA response, then enrollment will continue in Stage 2.

If the study/cohort proceeds to the second stage, additional patients with a deleterious BRCA1/2 mutation will be accrued for a total of 54. If there are at least 16 responses in 54 patients, the null hypothesis (ORR = 20%) will be rejected. Additionally, if the criteria for Stage 2 are met, additional patients, up to approximately 100 total, may be enrolled. Enrollment in Cohort B (BRCA1/2) will be halted when Cohort A (BRCA1/2) is fully enrolled.

Cohort B (ATM)

Patients in Cohort B (ATM), having a deleterious ATM mutation, will be enrolled concurrently with patients from Cohort B (BRCA1/2). It is expected that about 1/3 of the Cohort B patients will have deleterious ATM mutations. If 100 patients are enrolled in Cohort B (BRCA1/2), then approximately 50 patients would be expected to enroll into Cohort B (ATM).

A Simon 2-stage type futility rule will be employed in Cohort B (ATM). The Stage 1 analysis will be performed after the first 18 patients have either: a) completed 16 weeks of treatment; or b) discontinued treatment prior to completing. Enrollment into the study will continue while this analysis occurs. If $\leq 4/18$ patients in Stage 1 have a PSA response ($\geq 50\%$ decrease), the DMC will evaluate the overall benefit/risk for patients with deleterious ATM mutations in this cohort and make a recommendation whether further enrollment should be discontinued. If $\geq 5/18$ patients have a PSA response, then enrollment will continue in Stage 2. If there are at least 11 responses in 33 patients with a deleterious ATM mutation, the null hypothesis (ORR = 20%) will be rejected. Additionally, if the criteria for Stage 2 are met, additional patients, up to approximately 50 total, may be enrolled. Enrollment in Cohort B (ATM) will be halted when Cohort A (BRCA1/2) is fully enrolled.

Cohort C

Up to approximately 60 patients will be enrolled into Cohort C. Enrollment in Cohort C will be halted when Cohort A (BRCA1/2) is fully enrolled. Since this cohort will enroll patients that have 1 of several different deleterious HRR gene mutations, each gene will be examined separately. It is anticipated that < 6 patients will have a deleterious mutation in the same HRR gene; however, if enrollment of patients with a deleterious mutation in the same gene is higher than anticipated then enrollment will be held at 6 patients with any 1 deleterious gene mutation and a futility rule will be implemented such that if no responses are observed, then enrollment of patients with a deleterious mutation in that particular gene will be stopped, in consultation with the DMC.

